### **2.3.2 Potential Benefits**

Immediate potential benefits include a focused effort by the research team to ensure that an EGD is performed within 24 hours of ED presentation for all subjects who are admitted and within 72 hours for all subjects who are discharged from the ED. In addition, some subjects may avoid hospitalization and have their symptoms managed as an outpatient. Long-term potential benefits include better management of a condition that is common and can recur.

### **2.3.3 Discussion**

The typical primary care, urgent care or emergency care provider is unable to evaluate common and serious conditions of the gastrointestinal tract such as a bleeding peptic ulcer. As such, more than 80% of patients who present to US ED's with suspected bleeding in their upper GI tract require hospitalization, procedural sedation by an anesthesiologist, and a traditional tube-based upper endoscopy by a gastroenterologist. While this traditional process is safe and effective, it is not efficient for low-risk patients and not timely for all high-risk patients. The opportunity to bring VCE to the front-lines of US medical care will revolutionize how we manage upper GI bleeding and shed light on critical diseases that have heretofore been hidden from providers. This trial is an important step toward demonstrating that VCE is a safe and effective tool to risk-stratify upper GI bleeding and improve quality of emergency care for all patients.

### 3 OBJECTIVES

#### 3.1 Study Objectives

Our primary goal is to test whether ED Video Capsule Endoscopy (VCE) is able to safely discharge low risk patients for outpatient evaluation and management. Our secondary objective is to estimate the sensitivity and specificity of VCE compared to subsequent EGD in the detection of serious bleeding lesions in the upper gastrointestinal (GI) tract.

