During hospital admission, EGD will be performed on all subjects and hemostasis therapy applied as necessary. The study team decided against mandating that EGD be performed within 24 hours of hospital admission. This is a pragmatic trial. The longer the duration between the inpatient EGD and the ED VCE the greater the likelihood of discrepancy in the findings that may be due to a change in the lesion as part of its natural course or due to treatments delivered. However, the primary objective of the study is not to evaluate diagnostic accuracy of the ED VCE. The study team decided it was more important to enroll subjects in a timely manner than exclude subjects because the inpatient EGD was not completed within 24 hours.

For the experimental CERA group, subjects will be monitored for a minimum of 4 hours after ingestion. VCE will be undergo a formal review after completion of the VCE by a staff gastroenterologist with extensive experience in VCEs of the small bowel, colon, and esophagus. Both research personnel and the gastroenterologist will undergo a capsule training program organized by Medtronic and receive accreditation after the training.

11. Subjects in the experimental arm who have no sign of active bleeding, show no serious endoscopic findings on capsule, and have stable hemoglobin, blood pressure and heart rate for at least 4 hours will be discharged from the ED. Discharged CE patients will be scheduled to have an outpatient EGD within 3 days post discharge. Patients will be instructed to return to the ED sooner if signs of new bleeding develops. The Research Coordinator will facilitate setting up this appointment for the patient.

Any subject in the experimental arm with a positive VCE or a negative VCE but has a drop in Hemoglobin  $\geq 3$  at 4 hours or an elevated HR or low BP will be admitted. A hemoglobin drop between 2 and 3 will NOT automatically transfer patient to active control arm. In these cases, decision to proceed will be up to discretion of treating physician. We anticipate that all admitted patients in the experimental arm will undergo EGD in the hospital (same as AC arm.)

12. Primary Outcome: (1) Percent Discharged Home. Assumption is that 100% of Active Control / standard risk assessment will be admitted.
13. Secondary Outcome: Sensitivity and specificity of VCE compared to EGD

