14. Safety outcomes. Patient will be followed for clinical course and EGD results. Day 7 and Day 30, subject follow-up by telephone (if home) or in person (if still in hospital) to assess for adverse events or recurrent bleeding episode. (Form Used, *CHEER*: 6,7)
15. All VCE's will be re-read by offsite gastroenterologists who are blinded to the first interpretation and the patient.

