### **8.5 Cheer 5: EGD Data Collection Sheet**

This form is completed by the Gastroenterologist completing the EGD read Interpretation Form.

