### 18.10 EGD Data Collection

## Esophagogastroduodenoscopy (EGD) data collection

Date and Time EGD performed \_\_\_\_\_ Initials person filling out form \_\_\_\_\_

Where was EGD performed? Inpatient outpatient

Provider reading EGD \_\_\_\_\_

Rank of person performing EGD

Attending GI

Attending General Surgery

GI Fellow 1st Year

GI Fellow 2nd Year

GI Fellow 3rd Year +

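### The reference EGD is not protected from knowledge of the VCE result, so VCE sensitivity and specificity are at risk of review bias; that bias acts upward, but the net direction is uncertain

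*Combined protocol and SAP*

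**What the plan says.** Section 3.1 sets one secondary objective, to "estimate the sensitivity and specificity of VCE compared to subsequent EGD in the detection of serious bleeding lesions". Section 3.2.2 defines positive and negative results for each test, and section 11.3 plans the accuracy comparison.

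On who reads what, and with what knowledge:

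- **First VCE read.** Section 4.4 provides for a "formal review after completion of the VCE by a staff gastroenterologist with extensive experience in VCEs". The VCE result helps to decide disposition, before the EGD.
- **VCE re-read.** Section 4.4, step 15: "All VCE's will be re-read by offsite gastroenterologists who are blinded to the first interpretation and the patient". This is the only blinded read in the plan.
- **EGD read.** Section 8.5: "This form is completed by the Gastroenterologist completing the EGD read Interpretation Form". Neither this section, nor 4.4, nor 11.3, nor the form in 18.10 says whether that person may know the VCE result. The unmasking sentence in section 7.6 concerns a drug code and does not touch the EGD.
- **EGD setting.** Section 4.4, step 11: "Discharged CE patients will be scheduled to have an outpatient EGD within 3 days post discharge". For the others in that arm, "We anticipate that all admitted patients in the experimental arm will undergo EGD in the hospital". Controls are admitted and have their EGD during the stay. The EGD form asks "Where was EGD performed? Inpatient outpatient" but has no field for knowledge of the VCE.

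**The concern.** When the reference test is read with knowledge of the index test, borderline findings tend to be settled in favour of agreement. Several EGD items in 18.10 are graded by eye: Forrest IIb against IIc, whether pathology is incidental, and whether coffee-ground material is present. A capsule miss that is under-called at EGD counts as a true negative. A capsule false alarm that is over-called at EGD counts as a true positive. Both accuracy measures then look better than they are.

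The VCE result could reach the endoscopist in two ways. One is the VCE report, which nothing in the plan withholds. The other is the care pathway. As the plan is written, controls and subjects with a positive capsule are admitted, so a scheduled outpatient study EGD points to an experimental-arm subject whose capsule was not called positive.

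At stake is the credibility of the only secondary objective. The EGD class also feeds the high-risk/low-risk classification in 11.3. The rule that either modality can make a lesion high risk does not recover a lesion that both reads call negative.

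**Working it through.** The plan gives no figure for the accuracy objective, so there is none to reproduce. Its one power statement (11.2) concerns admission rates and is not affected by this point.

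**Inputs**

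- VCE subjects: 50, from 100 patients (11.2). The 1:1 allocation is an assumption, since the ratio is not stated.
- High-risk share: 20%, the upper limit anticipated in 11.2. This gives 10 high-risk and 40 low-risk subjects.
- True accuracy, set A: sensitivity 88%, specificity 64% (2.1, the 25-subject ED study; these are for fresh blood).
- True accuracy, set B: sensitivity 95%, specificity 92% (2.1, for high-risk lesions in capsules that reached the duodenum).
- q, the share of discordant EGD reads that move to the VCE class: not in the documents, assumed.
- The reference is EGD alone, as in 3.1. The index VCE read is taken to be the one the endoscopist may know; the plan does not say which VCE read is used.

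**Starting counts**

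- Set A: TP = 8.8, FN = 1.2, TN = 25.6, FP = 14.4.
- Set B: TP = 9.5, FN = 0.5, TN = 36.8, FP = 3.2.

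**All discordant pairs can shift**

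TP' = TP + q·FP; FN' = (1−q)·FN; TN' = TN + q·FN; FP' = (1−q)·FP.

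- Set A, q = 0.2: sensitivity = 11.68/(11.68 + 0.96) = 92.4%; specificity = 25.84/(25.84 + 11.52) = 69.2%.
- Set A, q = 0.5: sensitivity = 16.0/16.6 = 96.4%; specificity = 26.2/33.4 = 78.4%.
- Set B, q = 0.2: sensitivity = 10.14/10.54 = 96.2%; specificity = 36.90/39.46 = 93.5%.

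**Only false negatives shift**

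This is the leak that follows from the outpatient route itself. TP and FP stay as they are.

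- Set A, q = 0.2: sensitivity = 8.8/(8.8 + 0.96) = 90.2%; specificity = 25.84/(25.84 + 14.4) = 64.2%.
- Set A, q = 0.5: sensitivity = 8.8/9.4 = 93.6%; specificity = 26.2/40.6 = 64.5%.

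Nearly all of the rise in specificity therefore depends on false positives also moving, which requires the endoscopist to know of a positive capsule.

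**A competing bias**

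Let a share h of lesions resolve before the EGD (h is assumed), then apply the full shift with q = 0.1. Set A with h = 0.25:

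- Before the shift: TP = 6.6, FP = 2.2 + 14.4 = 16.6, FN = 0.9, TN = 0.3 + 25.6 = 25.9. Specificity is 25.9/42.5 = 60.9%.
- After the shift: sensitivity = 8.26/9.07 = 91.1%; specificity = 25.99/40.93 = 63.5%.

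Review bias raises specificity from 60.9% to 63.5%, yet the result is still below the true 64%. The same steps for set B give 95.8% and 88.0%, against a true 95% and 92%.

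**Could the data reveal it?**

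With about 10 high-risk VCE subjects, 9/10 has an exact 95% interval of 55% to 99.7%. Shifts of a few points could not be seen afterwards.

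**The case against.** The strongest reply is that this is inferred from silence. No section says that endoscopists receive the VCE report. The abbreviation list has a central reading group for endoscopy, 6.1 plans a real-time read group, and Appendix A mentions a central capsule reading team, so the VCE reader may well be separate from the local endoscopist. A reader might infer that one person reads both tests; the documents neither say so nor rule it out. The provider fields in 18.9 and 18.10 would already show it.

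A reader might also infer that the inpatient route reveals a positive capsule. It does not: inpatients include all controls, and experimental-arm subjects with a negative capsule who are admitted on hemoglobin, heart rate or blood pressure. The route discloses only non-positive results, and even that assumes every control has the EGD during the stay.

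The most tempting stronger reading is that sensitivity and specificity *are* biased upward. The documents do not support it. Section 4.4 itself warns: "The longer the duration between the inpatient EGD and the ED VCE the greater the likelihood of discrepancy in the findings". A lesion that resolves between the tests turns a correct capsule into a false positive. In 3.2.2, malignancy makes a VCE positive but is not on the positive EGD list, which also lowers specificity.

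Finally, 4.4 calls the trial pragmatic and says diagnostic accuracy is not the primary objective. Day 7 and Day 30 follow-up gives a check on missed lesions that does not depend on EGD grading.

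These replies limit the claim but do not remove it. The pragmatic argument is given for not requiring EGD within 24 hours, not for leaving the EGD read open. The other biases do not cancel review bias in any known way.

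**Conclusion.** The gap is real: the reference read of the only secondary objective has no stated protection from the index result, and the outpatient route hints at that result. The supportable conclusion is a risk of review bias that acts upward, with the net direction of error uncertain.

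Its size is unknown because q is not documented. At q = 0.2 it ranges from about 2 points on sensitivity and almost none on specificity (false negatives only, from 88%/64%) to about 4 and 5 points (all discordant pairs). From 95%/92% the full shift is worth about 1 and 1.5 points. These figures rest on 1:1 allocation, 20% high-risk prevalence and EGD alone as the reference.

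Percent discharged home and the stated sample size are unaffected. The point merits a change because the fix is cheap and the bias cannot be recovered from the data later.

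**What to change.** In 3.2.2, 11.3 and the EGD form (18.10):

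1. State that the endoscopist records items a to i from the first inspection before opening the VCE report or video, unless the treating team wants the VCE result first. In that case it is given and the fact recorded.
2. Add one tick box to the EGD form: *VCE result known before items a–i were completed*.
3. Identify same-reader cases from the existing provider fields in 18.9 and 18.10; no new field is needed.
4. Report sensitivity and specificity for all subjects, with a descriptive sensitivity analysis in those whose EGD was recorded without knowledge of the VCE and by a different reader.

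The cost is a short instruction, one box and one extra table; no subject is excluded. The downside is that the subset will be small and self-selected, so it can only be descriptive. The outpatient route will still hint at a non-positive capsule. The bias is reduced and documented, not removed.

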#### 3.2 Study Outcome Measures

3.2.1 Primary Outcome: (1) Percent Discharged Home. Assumption is that 100% of Active Control (AC) group will be admitted.

3.2.2 Secondary Outcome: Sensitivity and specificity of VCE compared to EGD. *Endpoints will be defined in the following way:*

Positive Video Capsule Endoscopy will be defined as:

1. Fresh blood or evidence of active bleeding visualized in upper GI tract.
2. Coffee ground blood visualized in upper GI tract, but no active bleeding seen.
3. A High Grade Non-Variceal Lesion (Forrest Ia, Ib, IIa or IIb).
4. Signs of Variceal Hemorrhage.
5. Signs of malignancy visualized in upper GI tract.

Negative VCE:

5. Clean stomach and duodenum, no fresh blood or coffee ground.
6. Upper GI pathology non-causative/ incidental.
7. A low grade non-Variceal lesion (Forrest IIc, III).

An Inconclusive VCE:

8. Any capsule that does not pass the pylorus before battery life is expired (and does not detect lesion in stomach or esophagus).

Positive EGD

1. Fresh blood or evidence of active bleeding.
2. Coffee ground but no active bleeding seen.
3. A High Grade Non-Variceal Lesion (Forrest Ia, Ib, IIa or IIb).
4. Signs of Variceal Hemorrhage.

Negative EGD

5. Clean stomach and duodenum, no fresh blood or coffee ground.
6. Upper GI pathology non-causative/ incidental.
7. A low grade non-variceal lesion (Forrest IIc, III).

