## **2.2 Rationale**

We believe there is an opportunity to improve the risk stratification of acute UGIB that presents to the Emergency Department through the use of Video Capsule Endoscopy. Our primary hypothesis is that VCE allows for safe outpatient management of ED patients with suspected upper GI hemorrhage. A multicenter randomized control trial is proposed to investigate the safety of this diagnostic modality.

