**Other Outcomes:**

1. Patient satisfaction with the VCE procedure. (Form Used: *CHEER #4*)

2. GI Physician Final Read and Site physician agreement of VCE results. (Form Used: *CHEER #5*)
3. Serious Adverse Events at Day 7 and Day 30 (Mortality, Re-Bleeding, Total Blood Transfusions, Surgery, Capsule-specific). (Form Used: *CHEER #7*)
4. ED Length of Stay (hours).
5. Hospital Length of Stay (days).
6. Cost-effective analysis.
  - At conclusion of study, we will construct a model using standard decision analysis software to examine the cost-effectiveness of three available strategies for a base-case patient who presents to the ED with either mild or moderate risk scenarios (by Glasgow-Blatchford Score) for requiring invasive hemostatic intervention (i.e., endoscopic, surgical, etc.) The three available diagnostic strategies are (1) direct imaging with video capsule endoscopy performed in the ED, (2) risk stratification using the Glasgow-Blatchford score, and, finally, (3) an admit-all strategy.

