### **7.2 Procedural Treatment Protocol**

### **7.3 Study Outcomes**

#### ***7.3.1 Primary Outcomes***

Our primary goal is to test whether ED Video Capsule Endoscopy (VCE) is able to safely discharge low risk patients for outpatient evaluation and management.

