### **11.3 Final Analysis Plan**

The analysis will be conducted in several stages. First, we will compare the baseline characteristics of the two study groups to determine if randomization was successful. We will also compare the baseline characteristics of the study samples by enrollment site. Second, we will compare the VCE and EGD results and classify all study subjects according to whether there is a high versus low risk lesion present. The VCE and EGD results may differ because they are not being performed at the same time and GI bleeds can resolve or change so it is unlikely that there will be perfect agreement between the two modalities. In cases where one modality identifies a low risk lesion and the other one a high-risk lesion, we will classify the lesion as high risk. If the VCE could not adequately visualize the tract, we will classify the results according to the EGD. We will compare the sensitivity and specificity of VCE and EGD for identifying high risk lesions. Finally, we will separately compare the admission rates of high-risk lesions and low risk lesions between the two study groups. We will compare admission rates aggregated across the four study centers as well as within each study center.

For tertiary outcomes, we will compare the outcomes by study group using a chi-square test statistic if the outcome is categorical such as the presence of an adverse event and a t test (normally distributed) or median test (non-normally distributed) if the outcome is continuous such as hospital or ED length of stay.

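### The stated goal is safe discharge, but the primary outcome is percent discharged with no condition on what follows, so the trial can meet it without showing safety

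*Combined protocol and SAP*

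**What the plan says.** The question is framed as one of safety in three places. Section 2.2: "Our primary hypothesis is that VCE allows for safe outpatient management of ED patients with suspected upper GI hemorrhage". Section 3.1: "Our primary goal is to test whether ED Video Capsule Endoscopy (VCE) is able to safely discharge low risk patients". Section 7.3.1, under the heading for primary outcomes, repeats the aim: "able to safely discharge low risk patients for outpatient evaluation and management". The Protocol Summary gives the same primary goal but leaves out the word safely.

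The outcome itself is a disposition. Section 3.2 has "Primary Outcome: (1) Percent Discharged Home", and section 4.4 repeats it: "Primary Outcome: (1) Percent Discharged Home. Assumption is that 100% of Active Control / standard risk assessment will be admitted". Neither places a condition on events after the patient leaves the ED. The sample size in section 11.2 is also based on admission rates.

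Safety data appear under Other Outcomes in section 3.2: "Serious Adverse Events at Day 7 and Day 30 (Mortality, Re-Bleeding, Total Blood Transfusions, Surgery, Capsule-specific". Section 11.3 treats these as tertiary outcomes, compared by arm "using a chi-square test statistic if the outcome is categorical such as the presence of an adverse event". It gives no acceptable rate, margin, confidence interval or power for that comparison. Sections 11.1 and 11.3 also compare admission of high-risk lesions between arms; section 11.2 concedes that power for this is unlikely to be adequate.

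**The concern.** In the primary tally, a capsule-arm patient who goes home and then re-bleeds, needs transfusion or dies counts the same as one who goes home and does well. The between-arm difference in that tally is also close to built in: the protocol admits every control and directs discharge of capsule-arm patients who meet its criteria. A positive primary result would show that the discharge pathway was followed and freed beds. It would not by itself support the hypothesis in section 2.2.

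The weight of that hypothesis then falls on the adverse-event comparison, which the plan neither sizes nor equips with a criterion. At stake is whether the final report can say anything quantitative about the safety of sending these patients home.

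**Working it through.** **Inputs.** From section 11.2: 100 subjects, 100% admission in controls, a 25-point difference among low-risk lesions, p < 0.05, and at most 20% high-risk lesions. From section 2.1: in the cited feasibility trial 7 of 37 capsule patients were admitted, so 30/37 = 81% were not. Assumed, because the documents do not say: 1:1 allocation, two-sided testing, and every adverse-event rate below.

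**1. The plan's own power figure.** With 20% high-risk lesions, 80 low-risk subjects remain, 40 per arm. For 100% v 75% the mean proportion is 0.875, and

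power = Φ{[0.25√40 − 1.96√(2 × 0.875 × 0.125)] / √(0.75 × 0.25)} = Φ{(1.581 − 0.917)/0.433} = Φ(1.53) = 93.8%.

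The exact Fisher figure is 95.7%. The stated power of at least 80% is confirmed for the admission endpoint.

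**2. What it takes to meet the primary outcome.** With 0 of 40 controls discharged and 6 of 40 capsule patients discharged, two-sided Fisher

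p = 2 × C(40,6)/C(80,6) = 2 × 3,838,380/300,500,200 = 0.026.

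Five discharges give p = 0.055, so six suffice. The p-value is the same whether none or all of the six re-bleed.

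**3. What the adverse-event test can detect.** Power at 50 per arm, by enumerating all outcome pairs at two-sided 0.05, with event rates taken over all subjects in each arm:

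| Assumed rates, control v capsule | Uncorrected chi-square | Fisher |
|---|---|---|
| 2% v 10% | 38% | 19% |
| 5% v 10% | 14% | 6% |
| 5% v 15% | 39% | 24% |
| 5% v 20% | 66% | 51% |

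At 2% v 10% the uncorrected test would miss a fivefold difference about 62% of the time (100 − 38).

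**4. What the discharged patients can show.** The exact (Clopper-Pearson) two-sided 95% upper limit for zero events in n patients is 1 − 0.025^(1/n); for x events it is the 97.5th percentile of Beta(x + 1, n − x).

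- About 40 discharged (81% of 50 = 40.5): 0 events, upper limit 8.8%; 2 events (5%), upper limit 16.9%.
- About 10 discharged (25% of 40 low-risk subjects, the difference used for sample size): 0 events, upper limit 30.8%.

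**The case against.** The strongest reply is that safety is far from ignored. Deaths, re-bleeding, transfusion, surgery and capsule events are prespecified and followed to Day 30. Section 2.3.1 names a major outcome after discharge as a potential major adverse event. Section 12 gives the DSMB a role in early cessation for harm. Discharge requires a capsule study without serious findings and at least four stable hours. The plan also compares admission of high-risk lesions, counting a lesion as high risk if either modality says so, and discharged patients are scheduled for EGD within three days; a high-risk patient sent home would therefore be visible. A disposition endpoint with separate safety reporting is a legitimate choice in a 100-patient trial, and the Protocol Summary's wording of the goal fits it.

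All of this stands, and it limits the point. A reader might infer that the trial does not address safety at all; the documents do not support that. What is missing is a role for safety in judging the primary question. The pre-discharge criteria are what is being tested, so they cannot also be the evidence, and the high-risk comparison is conceded to be underpowered.

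A reader might also infer that the plan intends to treat a non-significant chi-square as proof of safety. Section 11.3 says only that outcomes will be compared. The no-significant-difference wording in section 11.1 concerns admission of high-risk lesions, not adverse events. The point is that such a result could not carry that meaning, not that the plan gives it one.

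Finally, it is tempting to make discharged-and-event-free the primary outcome. Against controls with 0% discharge by design this would not show safety either: if 80% went home and 10% of those had an event, 0.80 × 0.90 = 72% v 0% would still be an overwhelming difference.

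**Conclusion.** The mismatch is real and remains in the current text: the question is safe discharge, and the primary outcome is discharge. The trial can meet its primary outcome without showing safety. Six discharges of 40 are enough, and the one between-arm test of adverse events has about 38% power at 2% v 10% (19% by Fisher).

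The discharged patients can still give a usable, if wide, bound: 8.8% to 16.9% with about 40 discharges and 0 to 2 events, and 30.8% with about 10 discharges and none. These figures rest on 1:1 allocation, two-sided 0.05, assumed event rates, and a discharge count taken either from the feasibility trial or from the planned difference. Other event rates change the numbers; across those tabulated, power never reaches 80%. The change should be made, but the data being collected are largely adequate for it.

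**What to change.** In sections 3.2 and 11.3, keep percent discharged and report with it the Day 30 rate, among discharged capsule-arm (CERA) subjects, of the events already listed (death, re-bleeding, transfusion, surgery) plus return admission for bleeding, with an exact 95% confidence interval. State that any safety conclusion rests on the upper confidence limit and not on a non-significant chi-square. The proportion discharged and event-free to Day 30 may be added as a descriptive companion. Align the goal's wording in the Protocol Summary with sections 2.2, 3.1 and 7.3.1.

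The cost is slightly more than wording. The Day 7/Day 30 follow-up form (section 18.12) asks about return visits and hospitalization for recurrent bleeding, but has no field for transfusion, surgery or death. Transfusion, surgery and a deceased disposition are on the chart review (section 18.13), which section 8.8 describes as covering the hospital stay; death can otherwise be recorded on the adverse event form. Add the three fields to the follow-up form, or complete the chart review to Day 30 for patients discharged from the ED. No extra patients or visits are needed. The headline conclusion may become less favourable.

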### ON THE ACCOMPANYING VIDEO CAPSULE ENDOSCOPY IS THERE EVIDENCE OF THE FOLLOWING? (Circle all that apply)

- a. Clean stomach and duodenum, i.e., no fresh blood or coffee ground
- b. Upper GI pathology non-causative/ incidental.
- c. A LOW grade non-Variceal lesion (Forrest IIc, III)
- d. A HIGH Grade Non-Variceal Lesion (Forrest Ia, Ib, IIa or IIb)
- e. Coffee ground blood
- f. Fresh blood or evidence of active bleeding
- g. Varices (either gastric or esophageal) or Variceal Hemorrhage
- h. Other sources of bleeding

-Mallory-Weiss

-Angiodysplasia

-Gastritis

-Esophagitis

-Tumor

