#### j. Did the capsule pass the pylorus before battery life expired (and does not detect lesion in stomach or esophagus.) Yes No

#### k. Based on your findings, would you recommend endoscopic hemostasis?

Yes

No

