### IN THE ACCOMPANYING EGD (ENDOSCOPY), IS THERE EVIDENCE OF THE FOLLOWING?

#### (Circle all that apply)

- a. Clean stomach and duodenum, i.e., no fresh blood or coffee ground
- b. Upper GI pathology non-causative/ incidental.
- c. A LOW grade non-Variceal lesion (Forrest IIc, III)
- d. A HIGH Grade Non-Variceal Lesion (Forrest Ia, Ib, IIa or IIb)
- e. Coffee ground blood
- f. Fresh blood or evidence of active bleeding.
- g. Varices (either gastric or esophageal) or Variceal Hemorrhage
- h. Other sources of bleeding

Other sources of bleeding

-Mallory-Weiss

-Angiodysplasia

-Gastritis

-Esophagitis

-Tumor

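### Malignancy makes a capsule read positive but appears in neither EGD list, so a bloodless tumour that both tests see cannot be scored as agreement

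*Combined protocol and SAP*

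**What the plan says.** The secondary outcome in section 3.2.2 is "Sensitivity and specificity of VCE compared to EGD". That section then lists what counts as positive and negative on each test.

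- **Positive VCE** has five criteria. The fifth is "Signs of malignancy visualized in upper GI tract".
- **Positive EGD** has four criteria, matching the first four for VCE: fresh or active blood, then "Coffee ground but no active bleeding seen", high-grade Forrest lesions and variceal haemorrhage. Malignancy is not there.
- **Negative VCE and negative EGD** have the same three criteria: a clean tract, incidental pathology, and "A low grade non-Variceal lesion (Forrest IIc, III"). Malignancy is in neither.
- **Inconclusive** exists for VCE only.

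Section 11.3 adds a separate rule. When one test shows a high-risk lesion and the other a low-risk one, the subject is classed as high risk. The same section plans sensitivity and specificity for high-risk lesions. It does not tie that term to the 3.2.2 lists or say whether the combined class serves as the reference.

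The read forms (18.9 for VCE, 18.10 for EGD) share items a to h, and readers circle all that apply. Item g is "g. Varices (either gastric or esophageal) or Variceal Hemorrhage". Item "h. Other sources of bleeding" covers Mallory-Weiss tear, angiodysplasia, gastritis, esophagitis and tumour. Item j on the VCE form asks "Did the capsule pass the pylorus before battery life expired (and does not detect lesion in stomach or esophagus"), with a single Yes/No.

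**The concern.** Sensitivity and specificity mean what they appear to mean only if test and reference use the same threshold, or if the difference is intended and stated. Here they differ by one criterion and no reason is given. The numbering hints at a slip: positive VCE runs 1 to 5 and negative VCE starts again at 5, while the EGD lists run 1 to 4 and 5 to 7. That is suggestive only.

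At stake is how one kind of patient is counted. Two endoscopic reads can agree completely on a tumour, yet no cell of the two-by-two table records the agreement. Where the patient goes depends on a reading that the plan does not supply, so the choice could be made after the results are known.

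**Working it through.** **Which figure to reproduce.** The plan gives no sample size or precision for sensitivity and specificity. Its only power figure (section 11.2, at least 80% for a 25-point difference in admission among low-risk subjects) concerns a different comparison. It holds: 100% against 75% with 40 low-risk subjects per arm gives 93.8% (pooled normal, two-sided 0.05). This point does not depend on it.

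**The lists side by side (section 3.2.2).**

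| Finding | VCE | EGD |
|---|---|---|
| Fresh or active blood | positive | positive |
| Coffee-ground material | positive | positive |
| High-grade Forrest lesion | positive | positive |
| Variceal haemorrhage | positive | positive |
| Malignancy | positive | not listed |
| Clean tract, incidental finding, low-grade Forrest lesion | negative | negative |

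A tumour with blood, coffee-ground material or high-grade stigmata on EGD is already EGD-positive. Only a tumour without them is affected.

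**Inputs for size.**
- 100 subjects (Protocol Summary); VCE in the experimental arm only (section 4.4, step 6).
- 1:1 allocation assumed, since no ratio is stated: 50 capsule subjects.
- At most 20% high-risk (section 11.2), used here as the EGD-positive share: 10 positive, 40 not positive.
- Assumed: both tests conclusive in all 50, VCE detects 9 of the 10 EGD-positives, and there are 3 other false positives.
- *k* = number of bloodless tumours seen by both tests. The documents give no rate, so 0 to 4 is shown.

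**One such tumour (*k* = 1) under each reading.**

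| Reading | Sensitivity | Specificity |
|---|---|---|
| As written, not positive scored as negative | 9/10 = 90.0% | 36/40 = 90.0% |
| As written, unclassified and dropped | 9/10 = 90.0% | 36/39 = 92.3% |
| Malignancy positive on both | 10/11 = 90.9% | 36/39 = 92.3% |
| Malignancy on neither list, scored negative on both | 9/10 = 90.0% | 37/40 = 92.5% |
| Section 11.3 either-modality class as reference, every VCE-positive counted as high risk | 13/14 = 92.9% | 36/36 = 100% |

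In the last row the 4 VCE-positive, EGD-not-positive subjects join the 10 EGD-positives, so 9 + 4 = 13 of 14 are detected. No VCE false positive is then possible, so specificity is 100% by construction.

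**Range over *k*.** Scored as in the first row, specificity is (37 − *k*)/40. With malignancy positive on both tests it is (37 − *k*)/(40 − *k*), and sensitivity is (9 + *k*)/(10 + *k*).

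| *k* | Specificity as written | Specificity, one list | Sensitivity as written | Sensitivity, one list |
|---|---|---|---|---|
| 0 | 92.5% | 92.5% | 90.0% | 90.0% |
| 1 | 90.0% | 92.3% | 90.0% | 90.9% |
| 2 | 87.5% | 92.1% | 90.0% | 91.7% |
| 3 | 85.0% | 91.9% | 90.0% | 92.3% |
| 4 | 82.5% | 91.7% | 90.0% | 92.9% |

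Each tumour costs 1/40 = 2.5 points of specificity as written. For scale, the Clopper-Pearson 95% interval at *k* = 0 (37/40) is 79.6% to 98.4%.

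**The forms.** Items a to f match 3.2.2 categories. Two gaps remain. A read with only item h circled has no stated class. Item g without e or f does not show whether there was haemorrhage, which is what 3.2.2 counts.

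**The case against.** The strongest reply is that the VCE list also serves as a triage rule, since section 4.4, step 11 uses a positive VCE for disposition. A triage rule may be broader than the condition it is tested against, and its specificity is then lower but still well defined. That is fair as a possibility, but the plan does not state the intent, and leaving malignancy off both EGD lists means the reference class itself is undefined for this patient.

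The reply also has weight on size. Section 4.4, step 10 says diagnostic accuracy is not the primary objective, known gastric cancer is excluded (section 5.2), and the shift per tumour is small beside the sampling error.

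A reader might infer more from the forms than they support.

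- *That the forms cause the mismatch.* They do not. Both share items a to h, including tumour, so one rule can be applied to both tests from the data collected.
- *That item j makes the inconclusive class impossible to derive.* Its wording joins two conditions, but the class is largely recoverable. If no blood or lesion is circled, a No can only mean the capsule did not pass. If a lesion in the stomach or esophagus is circled, the read is not inconclusive by definition.
- *That many subjects will have no class because of item h.* The documents give no frequency. Because readers circle all that apply, item h can simply name the source of a finding already coded under a to f. Only reads with h alone are open.
- *That item g is a large gap.* Bleeding varices would also be coded under e or f, and known varices and cirrhosis are excluded.

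**Conclusion.** The mismatch in section 3.2.2 stands: malignancy is positive on VCE and absent from both EGD lists, so a bloodless tumour seen by both tests can never count as agreement. On 40 EGD-negative subjects the cost is about 2.5 specificity points per tumour. This rests on 1:1 allocation, the 20% ceiling taken as the EGD-positive share, and conclusive reads in all subjects. The number of such tumours is unknown and probably small; with none, the effect is zero. Severity is minor to moderate, on a secondary outcome.

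Two stronger conclusions are tempting. One is that such a patient is a VCE false positive as a matter of course. The text does not settle that: strictly the EGD is unclassified, the false positive needs not-positive to be read as negative, and section 11.3 could turn the same patient into a true positive if its rule is the reference and malignancy counts as high risk. The other is that the high-risk and low-risk groups for the admission comparison are shown to be distorted. Sections 11.1 to 11.3 never link those terms to the 3.2.2 lists, so this cannot be concluded. The percentage discharged and its stated power do not depend on how the accuracy table is scored.

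**What to change.** 1. In section 3.2.2, for the sensitivity and specificity analysis only, use one positivity list for both tests, with malignancy in both or in neither. If in neither, state the class of a tumour-only read on each test. The use of a positive VCE for disposition in section 4.4, step 11 is left as it is.
2. In section 11.3, state that EGD alone is the reference for accuracy, and that the either-modality class is not used for it.
3. Before analysis, fix in a short table, identically for VCE and EGD, how reads with only item h, or with item g but neither e nor f, are classed.
4. Reword item g on both forms so that variceal haemorrhage is recorded on its own, and item j on the VCE form so that pylorus passage is recorded on its own.

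The cost is a few lines of protocol text, one mapping table and small edits to two forms. No extra procedures are needed. Section 16.1 treats the recorded videos and hospital records as source data, and all capsule studies are to be re-read by blinded offsite gastroenterologists (section 4.4, step 15), so reads already made can be recoded.
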